12.1. INFORMED CONSENT	37
12.2. INSTITUTIONAL REVIEW BOARD	37
12.3. AMENDMENTS TO THE PROTOCOL	37
12.4. DATA RECORDS.....	37
13. PUBLICATION AND AGREEMENT	38
14. INVESTIGATORS AGREEMENT	38
15. REFERENCES	39
16. APPENDICES	40

CLINICAL PROTOCOL SUMMARY SHEET

STUDY TITLE: A Safety and Efficacy Comparison of BLI4700 Bowel Preparation versus an FDA-approved Comparator in Adult Subjects prior to Colonoscopy

PROTOCOL: BLI4700-302

VERSION DATE: 7-28-17

IND NUMBER: 124,988

STUDY PHASE: 3

OBJECTIVE: To compare the safety and efficacy of BLI4700 bowel preparation to PREPOPIK as 2-day, split-dose bowel preparations prior to colonoscopy in adult patients.

STUDY DESIGN: This will be a randomized, parallel, multi-center, single-blind study.

SUBJECTS: Approximately 400 male and female adult subjects will be enrolled and undergo colonoscopy. It is anticipated that approximately 450 subjects will be randomized to achieve 400 completed colonoscopies.

STUDY MEDICATIONS: Treatment 1: BLI4700 bowel preparation
Treatment 2: PREPOPIK

DURATION: Subject participation in this study may last up to 60 days.

EFFICACY ENDPOINTS: Efficacy will be based on overall preparation success as determined by the blinded colonoscopist. Additional efficacy measures include the proportion of excellent preparations, segmental cleansing, time to cecum, volume of intraprocedural water used to improve visualization, percent of procedures that reach the cecum.

SAFETY ENDPOINTS: Safety endpoints include:

- Adverse event reports
- Changes in serum chemistry and hematology parameters
- Subject reported prep-related symptoms
- Orthostatic heart rate and blood pressure

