4. STUDY PROCEDURES

Study procedures are described as follows and depicted graphically in Section 4.5, below.

4.1. Visit 1

At the screening visit, the following procedures will be undertaken:

- Subject is fully informed about the study and gives written agreement to study participation in the form of a signed informed consent form (refer to Section 4.1.1) and assign a subject number
- Assess eligibility (refer to inclusion/exclusion criteria)
- Review of medications
- Medical history - medical history will be recorded to include all ongoing conditions at Visit 1 as well as any significant conditions, defined as:

Abdominal surgeries, Renal failure/dysfunction, Liver failure/dysfunction, Cardiac disorders (e.g. myocardial infarction, coronary artery disease tachycardia), Hypertension, Diabetes, Cancer (must indicate type of cancer), Electrolyte abnormalities

- Physical examination
- Vital signs: including assessment of orthostatic hypotension (while seated and after standing for a minimum of 2 minutes) including height and bodyweight, pulse, respiratory rate and temperature
- A 12-lead ECG will be performed by qualified, trained site personnel. ECG output must be reviewed by a physician investigator. Any clinically significant cardiac abnormalities identified on the ECG should disqualify a subject. Data from the ECG will be collected in the eCRF.
- Blood samples will be collected for testing at a central laboratory, as shown below.

Serum Chemistry: ALT, anion gap (calculated), AST, bicarbonate, total bilirubin, blood urea nitrogen, calcium, chloride, creatine kinase, creatinine, eGFR (calculated), GGT, magnesium, phosphorus, potassium, sodium, sulfate (Visits 1, 2 and 3 only), total protein, uric acid and osmolality. Creatine kinase results > 2.5 times the upper normal limit will trigger a test for CK-MB.

Hematology: Basophils, HCT, HGB, Lymphocytes, MCH, MCV, MPV, Neutrophils, Platelets, RBC, WBC

Urinalysis: dipstick analysis (Visits 1, 2 and 3 only). Urine positive for bacteria will require follow-up if the investigator believes the result is due to urinary tract infection.

Investigators will be instructed to comment on all out of range values for clinical significance. For critical values (those indicative of a potential safety concern), investigators will be contacted by the central laboratory. Critical value alert levels are listed in the laboratory manual.

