4.1.6. Subject Questionnaires

Subjects will be provided with a Preparation Questionnaire and Dietary Questionnaire to document their preparation and dietary intake (refer to Appendix A for full

questionnaires). Subjects will complete the Dietary Questionnaire starting the day before the colonoscopy. Completion of the Preparation Questionnaire will commence with Dose 1 on the day before colonoscopy and continue through the completion of the required clear liquids after Dose 2 the following day. The time of all food/fluid ingestion will be recorded. Site staff must review the descriptions and times recorded on the questionnaire at Visit 2 to confirm that subjects were compliant with the dietary restrictions outlined in Section 4.1.4.

Subjects that take any amount of bowel preparation (but do not have a colonoscopy performed) should still return for safety follow-up as outlined in Sections 4.2 – 4.4.

4.2. Visit 2

After completing both preparation doses, subjects will return to the study center for their colonoscopy. Sites should attempt to schedule subjects a minimum of 4 days from date of screening to allow for receipt and review of screening lab results up to a maximum of 30 days. Visits scheduled beyond 30 days from Visit 1 will be considered a protocol violation and subjects must have a repeat blood draw. Due to follow-up requirements for laboratory testing within 24 – 48 hours of Visit 2 (See Section 4.3), colonoscopies may not be performed on a Friday unless the research center is open on Saturday or Sunday to collect a follow-up blood sample.

Subjects will bring back their questionnaires and study personnel will review the questionnaires for completeness so that any missed responses can be captured. Any violations of the dietary restrictions must be confirmed with the subject. Study personnel will perform drug accountability as described in Section 4.2.1.

Vital signs will be taken. A 12-lead ECG will be performed by qualified, trained site personnel. ECG output must be reviewed by a physician investigator and subjects with a clinically significant abnormal result must be discontinued prior to colonoscopy. A physical examination will be performed. Subjects will be queried for expected preparation symptoms using the Symptom Scale (see Section 4.2.2) or changes to their concomitant medications. Subjects will complete a Preference Questionnaire (See

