Appendix A). Blood samples for chemistry and hematology testing will be taken as outlined in Section 4.1.

The colonoscopy will be performed by a physician according to the site's standard procedures and evaluated on a 4-point scale, as shown in Section 4.6. The colonoscopy procedure will be video recorded. A designated vendor will provide standardized video recording capabilities and centralized reading by an independent gastroenterologist. A subset of colonoscopies will be reviewed and graded by the central reader for the primary endpoint (overall cleansing assessment). The procedures and requirements for recording and transmitting colonoscopy videos will be outlined in a separate manual.

Endoscopists should limit the use of water flush to that necessary to achieve the cleansing required to achieve adequate visualization. Water immersion and/or exchange technique should be avoided unless it is medically indicated.

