4.3. Visit 3: 24 – 48 Hours Post Colonoscopy

Subjects will return 24 – 48 hours following colonoscopy for follow-up. Blood samples will be collected for serum chemistry and hematology testing. Subjects will be queried for occurrence of adverse events and changes in concomitant medications. Subjects will be queried for information pertaining to the onset and treatment of serious adverse events occurring following the colonoscopy, and adverse events that were ongoing at Visit 2. Vital signs will be taken. A 12-lead ECG will be performed by qualified, trained site personnel. ECG output must be reviewed by a physician investigator. Subjects with abnormal and clinically significant ECG results at Visit 3 must return for follow up visits as outlined in Section 4.4.

Subjects that miss Visit 3 must return for follow-up Visit 4. If these subjects have no out of range laboratory values (that were not pre-existing at Visit 1) and/or ongoing adverse events at Visit 4, Day 30 follow-up may be performed via telephone (See Section 4.4.1).

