4.4. Visits 4 and 5: Follow up of Adverse Events and Laboratory Results

Subjects with out of range laboratory values (that were not pre-existing at Visit 1) and/or ongoing adverse events at Visit 3 will return for follow up on Day 7 (+/- 2 days) and Day 30 (+/- 2 days). Subjects requiring follow-up for abnormal laboratory values must undergo repeat testing. Subjects returning due to ongoing adverse events should be assessed to determine if the event has resolved or is clinically stable.

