4.5. Tabulated Study Procedures

The following graphically depicts the flow of study procedures at each visit.

Procedures	Visit 1 Screening	Day before colonoscopy	Visit 2 Day of colonoscopy	Visit 3 24-48 hrs post colonoscopy	Visit 4 Day 7 (+/- 2 days) *if needed*	Visit 5 Day 30 (+/- 2 days) *if needed*	Day 30 ⁴ (+/- 2 days) *if by telephone*
Informed Consent	X						
Inclusion/Exclusion Criteria Review	X						
Medical History	X						
Physical Examination	X		X				
Vital Signs (including ECG)	X		X	X	X	X	
Review of Concomitant Medication	X		X	X	X	X	X
Blood Collection for Laboratory Testing	X		X	X	X	X	
Urine Collection for Laboratory Testing	X		X	X			
Serum Pregnancy Test (if applicable) ¹	X						
Treatment Assignment ²	X						
Dispense Drug and Questionnaires ²	X						
Subjects Begin Questionnaires		X					
Subjects Take Bowel Preparations		X	X				
Symptom Scale & Preference Questionnaire Completed ³			X				
Drug Accountability ²			X				
Colonoscopy performed with Intra-procedural Safety and Efficacy Grading			X				
Collect and assess adverse event data			X	X	X	X	X

¹ refer to Section 4.7 ²to be performed by unblinded personnel only ³to be completed at Visit 2 prior to sedation

⁴Day 30 follow-up may be performed by telephone for subjects with no new or ongoing AEs or lab abnormalities at Visit 3

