9.2. Study Endpoints - Safety

Adverse Events:

All subjects who took preparation in any amount will be included in the safety analysis. All adverse events will be analyzed based on the principle of treatment emergence. A sign or symptom will be regarded as treatment-emergent if it was present prior to the first dose and subsequently worsened in severity, or was not present prior to the first dose but subsequently appeared.

In order to define treatment emergence for events with missing start or stop dates the following additional criteria will be used:

- if both the onset and resolution dates for a particular event are missing, then the event is considered treatment-emergent;
- if the onset date for an event is missing and the resolution date falls after the initiation of the first dose, then the event is considered treatment-emergent;
- if the onset date for an event falls after the initiation of the first dose and the resolution date is missing or present, then the event is considered treatment-emergent; and
- if the onset date for an event falls before the initiation of the first dose and the stop date is missing or present, then the event is not considered treatment-emergent.

Adverse events will be collected using MedDRA category designations for body system and preferred term. The number and percent of subjects who experienced each adverse event will be presented in a tabular form. Individual tables will be provided for treatment-emergent adverse events, treatment-emergent adverse events by relationship to study drug, and treatment-emergent adverse events by severity. The difference in adverse events between study populations will be tested by the Fisher's exact test together with a 95% confidence interval for the treatment effect estimate.

Vitals Signs and Physical Examination:

Vital signs and physical examination data will be summarized with descriptive statistics.

Laboratory Data:

Results of laboratory tests for the change from baseline (Screening) and treatment group differences will be tested using ANOVA. In addition, shift tables will be presented to describe changes in lab parameter values between screening and post-treatment time points using normal range categories (low, normal, high).

Symptom Scale Data:

Symptom Scale data for individual symptoms for Overall Experience (stomach cramping, stomach bloating, nausea and vomiting) will be presented categorically by severity and tested by Chi-Square test.

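### Laboratory change from screening is compared between arms by ANOVA with no baseline covariate; adding the screening value (ANCOVA) would tighten the estimates at almost no cost

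*Combined protocol and SAP*

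**What the plan says.** The Clinical Protocol Summary Sheet lists "Changes in serum chemistry and hematology parameters" among the safety endpoints. Section 9.2 (Laboratory Data) gives the analysis: "Results of laboratory tests for the change from baseline (Screening) and treatment group differences will be tested using ANOVA". Shift tables by normal-range category are added. No model terms are stated for this ANOVA. The only ANOVA whose terms are given is the one for continuous secondary efficacy endpoints in Section 9.1 (treatment, site and their interaction), and it has no baseline term either.

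The screening value is available for everyone. At Visit 1 (Section 4.1), "Blood samples will be collected for testing at a central laboratory, as shown below". The panel is drawn again at Visit 2 (Section 4.2: "Blood samples for chemistry and hematology testing will be taken as outlined in Section 4.1") and at Visit 3 (Section 4.3: "Blood samples will be collected for serum chemistry and hematology testing"). The row "Blood Collection for Laboratory Testing" in the Section 4.5 table confirms this schedule.

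Two further provisions matter for the fix. On late colonoscopies, Section 4.2 says: "Visits scheduled beyond 30 days from Visit 1 will be considered a protocol violation and subjects must have a repeat blood draw". Attendance at Visits 4 and 5 depends on findings at Visit 3 (Section 4.4): "Subjects with out of range laboratory values (that were not pre-existing at Visit 1) and/or ongoing adverse events at Visit 3 will return".

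**The concern.** The screening value is subtracted from the post-dose value but is not in the model. Subtraction removes the right amount of baseline variation only if the regression slope of post-dose on screening is 1. At any other slope, part of the baseline variation stays in the error term, and the between-arm estimate is less precise than the same data allow.

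At stake is the precision of the arm differences on a named safety endpoint, and nothing beyond that. Section 9.3 sizes the trial on preparation success alone, so no laboratory hypothesis is powered and no loss of power is claimed. The safety of individual subjects is covered separately, by critical-value alerts (Section 4.1) and repeat testing (Section 4.4). Chance baseline imbalance between arms is part of the same variance and is not a second harm.

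**Working it through.** **Plan's own figure.** There is none to reproduce: the documents give no SD, correlation, power or sample size for the laboratory comparison.

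**Inputs from the plan.** About 400 subjects assigned 1:1, 200 per group (Section 9.3); change-score ANOVA with no stated covariate (Section 9.2).

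**Assumed inputs.** Screening SD set to 1; post-dose SD = k; screening/post-dose correlation = r. Ranges: r = 0.3 to 0.9; k = 0.8, 1 and 1.25.

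**Formulas.**
- Variance per subject, change score: 1 + k² − 2kr
- Variance per subject, ANCOVA: k²(1 − r²)
- Difference between the two: (1 − kr)², which is never negative and is zero only when the slope kr equals 1
- 95% CI half-width for the arm difference: 1.96 × √(2 × variance / 200)

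**Worked case, k = 1, r = 0.5.** The change-score variance is 1 + 1 − 1 = 1.00, with half-width 1.96 × √0.0100 = 0.196. The ANCOVA variance is 1 − 0.25 = 0.75, with half-width 1.96 × √0.0075 = 0.170. The variance ratio is 0.75 and √0.75 = 0.866, so the interval is 13.4% narrower.

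**Equal SDs (k = 1; the ratio reduces to (1 + r)/2).**

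| r | Variance ratio | Half-width, change score | Half-width, ANCOVA | CI narrower by |
|---|---|---|---|---|
| 0.3 | 0.65 | 0.232 | 0.187 | 19.4% |
| 0.5 | 0.75 | 0.196 | 0.170 | 13.4% |
| 0.7 | 0.85 | 0.152 | 0.140 | 7.8% |
| 0.9 | 0.95 | 0.088 | 0.085 | 2.5% |

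Half-widths are in screening SDs. Dividing 400 by the ratio gives the number of subjects that change-score ANOVA would need for the same precision: about 615, 533, 471 and 421.

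**Unequal SDs.**

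| k | r = 0.3 | r = 0.5 | r = 0.7 | r = 0.9 |
|---|---|---|---|---|
| 0.8: variance ratio | 0.502 | 0.571 | 0.628 | 0.608 |
| 0.8: CI narrower by | 29.1% | 24.4% | 20.8% | 22.0% |
| 1.25: variance ratio | 0.784 | 0.893 | 0.981 | 0.950 |
| 1.25: CI narrower by | 11.4% | 5.5% | 1.0% | 2.5% |

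**Worst case.** At k = 1.25 and r = 0.8 the slope is 1 and the ratio is 1.00. The finite-sample variance factor for one covariate is 1 + 1/(400 − 4) = 1.0025, so the interval is wider by √1.0025 − 1, about 0.13%.

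**Simulation check (200 per arm).** Simulated ANCOVA/change-score variance ratios at k = 1 were 0.66, 0.73, 0.84 and 0.96 for r = 0.3, 0.5, 0.7 and 0.9, and 1.00 at the no-gain point. Type I error was 4.3% to 5.6% across both models. With different slopes in the two arms, ANCOVA still had the smaller variance: ratio 0.78 for slopes 0.9 and 0.3, and 0.94 for slopes 1.2 and 0.4.

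**The case against.** The strongest case is about weight. The planned test is valid and unbiased, no study conclusion rests on it, and the size of the gain is assumed throughout. For strongly correlated analytes, or where post-dose values are more variable than screening values, the gain can be 1% to 2.5% or nothing. Section 3.5.2 also restricts screening sodium, potassium and magnesium while post-dose values are unrestricted. For those electrolytes this pushes k upward, so the k = 0.8 figures are optimistic. All of this stands, and it limits how much should be claimed.

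Section 9.2 promises a test for laboratory data and not a confidence interval, so the narrower interval becomes visible only once the fix adds one. That is also correct. The variance reduction applies to the test as well, but no powered hypothesis depends on it.

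The absence of a covariate is inferred from a section that states no model terms at all, and Section 9.4.3 mentions a statistical analysis plan. That reference concerns reasons for exclusion from the per-protocol population. Nothing in the documents available supplies a laboratory model. If a separate plan already specifies ANCOVA, no change is needed. If site terms were included, the degrees of freedom would differ from 398, but the covariate would still cost one.

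Finally, a linear model on the raw scale may suit skewed analytes such as creatine kinase poorly. The planned ANOVA on raw change has the same exposure, and a check with lognormal values still favoured ANCOVA (variance ratio about 0.75 to 0.77).

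**Conclusion.** The point holds as a recommended improvement. The plan leaves out of the model a baseline value that it already holds. Under equal SDs and correlations of 0.3 to 0.9, confidence intervals for the laboratory arm differences would be about 19% to 2.5% narrower. Across the wider range examined, the result runs from 29% narrower to 0.1% wider, the latter only where the slope on screening is 1. These figures rest on assumed r and k, 200 per arm with laboratory data, and a linear relation to the screening value. The gain will differ by analyte and applies to the between-arm comparison, not to the shift tables.

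**What to change.** In Section 9.2, for each continuous chemistry and hematology parameter, estimate the between-arm difference in change from screening at Visit 2 and at Visit 3 by ANCOVA, with treatment as factor and the screening value as covariate. Report each difference with a 95% confidence interval.

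Define the screening value once: Visit 1, or the last value drawn before the first dose where Section 4.2 requires a repeat draw. That section does not say when the repeat is taken relative to dosing, so the rule should be explicit. Use the same value for the change, the covariate and the shift tables.

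Keep the within-arm change as a summary (mean, SD, 95% confidence interval) and keep the shift tables. Leave Visits 4 and 5 descriptive, because attendance is selective: subjects return because of abnormal results, ongoing events or a missed Visit 3.

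The cost is analysis-plan wording and model code, plus one degree of freedom per model. No new data are needed.

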3.5.2. Exclusion Criteria

Subjects who meet any of the following criteria will be excluded from the study:

1. Subjects with dysphagia or an aversion to swallowing tablets.
2. Subjects with known or suspected ileus, gastrointestinal obstruction, gastroparesis, gastric retention, bowel perforation, toxic colitis or megacolon.
3. Subjects with ongoing severe, acute inflammatory bowel disease
4. Subjects who had previous significant gastrointestinal surgeries (e.g. colostomy, colectomy, gastric bypass, gastric banding, stomach stapling). Any questions regarding the significance of a previous gastrointestinal surgery should be directed to Braintree Laboratories.
5. Subjects with uncontrolled pre-existing electrolyte abnormalities, or those with clinically significant electrolyte abnormalities based on Visit 1 laboratory results.

Subjects with Visit 1 laboratory results outside the following ranges will be excluded regardless of investigator assessment of clinical significance:

- Serum sodium > 150 mmol/L or < 132 mmol/L
- Serum potassium > 5.5 mmol/L or < 3.5 mmol/L
- Serum magnesium > 2.7 mg/dL or < 1.2 mg/dL

6. Subjects taking diuretics, anti-hypertensive medications, including angiotensin converting enzyme (ACE) inhibitors and Angiotensin II receptor blockers (ARBs), or chronic NSAIDs, that have not been stable for 30 days. NSAID use for occasional pain is not exclusionary.
7. Subjects with uncontrolled hypertension (systolic blood pressure > 170 mmHg and diastolic blood pressure > 100 mmHg).
8. Subjects taking antibiotics within 7 days of colonoscopy.
9. Subjects with severe renal insufficiency (GFR < 30 mL/min/1.73m²).
10. Subjects with known severe hepatic insufficiency (Child Pugh C)
11. Subjects with cardiac insufficiency (NYHA Functional Classifications 3 or 4).
12. Subjects with an abnormal and clinically significant physical examination or ECG finding at Visit 1.
13. Subjects undergoing insulin therapy for any indication.

14. Subjects with impaired consciousness that predisposes them to pulmonary aspiration.
15. Subjects undergoing colonoscopy for foreign body removal and/or decompression.
16. Subjects who are pregnant or lactating, or intending to become pregnant during the study.
17. Subjects of childbearing potential who refuse a pregnancy test.

Subjects allergic to any BLI4700 components

19. Subjects using drugs of abuse, including abused prescription medications.
20. Subjects who are withdrawing from alcohol or benzodiazepines.

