5. ADVERSE EVENTS

5.1. Adverse Event Definition and Reporting

An Adverse Event (AE) is any untoward medical occurrence associated with the use of a drug in humans, whether or not considered drug related. An AE can therefore be any unfavorable and unintended sign (including a clinically significant abnormal laboratory finding), symptom, or disease temporally associated with the use of a medicinal (investigational) product. Subjects will be queried for any problems they experienced during and after preparation by site personnel. Any symptom on the symptom scale rated as mild, moderate or severe must be reported as an adverse event. Colonoscopy and biopsy findings are not considered adverse events unless considered by the investigator to be related to the preparation or colonoscopy procedure.

Adverse event collection will commence at the time the patient provides informed consent and conclude 30 days after preparation exposure.

Subjects will be instructed to promptly report adverse events to the Investigator. The Investigator will record date/time of report, date/time of onset, description of the adverse event, severity of adverse event, action(s) taken regarding treatment of the event, action(s) taken regarding study participation, duration of adverse event, and the Investigator's assessment of relationship of adverse event to study preparation.

The Investigator should assess the severity of each adverse event using the following categories:

Grade	Severity	Description
1	Mild	Barely noticeable, does not influence functioning causing no limitations of usual activities
2	Moderate	Makes participant uncomfortable, influences functioning causing some limitations of usual activities
3	Severe	Severe discomfort, treatment needed Severe and undesirable, causing inability to carry out usual Activities
4	Life threatening	Immediate risk of death, Life threatening or disabling (Must be reported as serious adverse event)
5	Fatal	Causes death of the participant (Must be reported as serious adverse event)

The Investigator should assess the relationship to study drug for each adverse event using the following categories:

Categories of Attribution:	Description
UNRELATED	There is no evidence of any causal relationship.

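### The planned laboratory analyses in 9.2 (mean change and a low/normal/high shift) cannot separate marginal from critical values and show no shift when a subject already out of range worsens

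*Combined protocol and SAP*

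**What the plan says.** The protocol summary sheet lists "Changes in serum chemistry and hematology parameters" among the safety endpoints. Section 9.2, under Laboratory Data, gives the whole analysis in two sentences:

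- "Results of laboratory tests for the change from baseline (Screening) and treatment group differences will be tested using ANOVA".
- "shift tables will be presented to describe changes in lab parameter values between screening and post-treatment time points using normal range categories (low, normal, high".

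It defines no grade, no critical threshold, no count of subjects beyond a threshold and no worst post-dose value.

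Elsewhere the protocol does use thresholds:

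- Section 3.5.2 sets numeric entry limits for sodium ("Serum sodium > 150 mmol/L or < 132 mmol/L" excludes), potassium and magnesium, and excludes "Subjects with severe renal insufficiency (GFR < 30 mL/min/1.73m²").
- Section 4.1 provides for alerts: "For critical values (those indicative of a potential safety concern), investigators will be contacted by the central laboratory". It places the alert levels in the laboratory manual.
- Section 8.3 puts cardiac, renal and metabolic terms under a graded stopping rule.

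Section 5.1 gives a second reporting route, because an adverse event includes "any unfavorable and unintended sign (including a clinically significant abnormal laboratory finding"). Section 9.2 tabulates treatment-emergent events by severity and by relationship, and compares arms by Fisher's exact test with a 95% confidence interval.

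**The concern.** The entry limits and the stopping rule show that the sponsor regards electrolyte and renal disturbance as a risk to watch. Harm of that kind would be expected as a large change in a few subjects, not a small change in everyone. Neither planned laboratory analysis is suited to showing it. An average dilutes a few large changes, and a table built "using normal range categories (low, normal, high") discards how far outside the range a value lies.

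Subjects who start out of range are served worst, since deterioration in the same direction leaves them in the same category. The entry limits can admit such subjects: sodium from 132 to 150 mmol/L, magnesium from 1.2 to 2.7 mg/dL and GFR of 30 or above, provided that an electrolyte abnormality was not judged clinically significant.

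At stake is whether the laboratory tables could tell a preparation that produces critical values from one that nudges values across a range limit.

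**Working it through.** The plan states no figure for this point, so there is none to reproduce. The check has three parts. Reference ranges, SD and effect sizes are assumptions, because the documents give none.

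**1. What the three categories can show.** Assumed ranges: sodium 135–145 mmol/L, potassium 3.5–5.0 mmol/L, magnesium 1.7–2.4 mg/dL, eGFR low below 60. All baselines below lie within the 3.5.2 numeric entry limits.

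| Analyte | Visit 1 → post-dose | Reads as |
|---|---|---|
| Sodium | 140 → 134 | normal to low |
| Sodium | 140 → 120 | normal to low |
| Potassium | 4.2 → 3.4 | normal to low |
| Potassium | 4.2 → 2.5 | normal to low |
| Sodium | 133 → 122 | low to low (no shift) |
| eGFR | 55 → 31 | low to low (no shift) |
| Magnesium | 2.6 → 4.5 | high to high (no shift) |

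The particular values depend on the assumed ranges. The pooling does not: any three-category table behaves this way.

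**2. What the mean can show.** Inputs: 200 per arm (section 9.3); assumed SD of sodium change 2.5 mmol/L; assumed loss of 10 mmol/L in a fraction f of one arm and no effect elsewhere.

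- Mean difference = f × 10.
- Variance in the affected arm = 2.5² + f(1 − f) × 10².
- SE = √(affected-arm variance/200 + 6.25/200).

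Six subjects (f = 0.03): difference 0.30; variance 6.25 + 2.91 = 9.16; SE = √(9.16/200 + 6.25/200) = 0.278; ratio 1.08; two-sided 5% power about 19%.

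Four subjects (f = 0.02): difference 0.20; variance 6.25 + 1.96 = 8.21; SE 0.269; ratio 0.74; power about 11.5%.

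**3. What a threshold count would show.** If the true rate of a marked change is 1% or 2%, the chance that an arm of 200 has at least one such subject is 1 − 0.99²⁰⁰ = 86.6% or 1 − 0.98²⁰⁰ = 98.2%. The count puts those subjects on the page.

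As a test it is modest. With none in the comparator arm, two-sided Fisher p-values are 0.12 for 4 versus 0, 0.061 for 5 versus 0 and 0.030 for 6 versus 0. Significance therefore needs at least 6 cases. At a true 2% rate against zero, the chance of 6 or more in 200 is about 21%.

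**The case against.** The strongest objection is that laboratory safety has other routes. Clinically significant findings are adverse events, graded, tabulated by severity and compared between arms. Investigators must comment on every out-of-range value and are alerted to critical ones. New out-of-range values at Visit 3 lead to repeat testing under section 4.4, and the stopping rule covers renal and metabolic terms. A reader might infer from 9.2 that a marked laboratory change would go unreported. The documents do not support that.

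The objection does not remove the gap. Whether a value becomes an adverse event is the investigator's judgement, with no numeric rule. The 5.1 severity grades describe symptoms and limits on activity, so a marked but silent change could be graded mild. The 4.4 follow-up trigger covers values that were not already out of range at Visit 1, so it passes over the same subjects whom the shift table misses.

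A reader might also infer that these judgements are made by openly unblinded staff. Section 4.1.2 names only the colonoscopist as blinded, but it also tells subjects not to discuss their assignment with study staff. Section 4.2.1 confines drug returns to designated unblinded personnel and treats a failure of staff blinding as a violation. The point does not need that inference.

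Three further objections stand and shape the remedy:

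- Entry limits are not critical levels. On the assumed range, a potassium cut at 3.5 would coincide with the lower limit of normal.
- A category boundary at GFR 30 would still show eGFR 55 → 31 as no shift.
- A Fisher test on 4 versus 0 is not significant either.

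Finally, section 9.4.3 refers to a statistical analysis plan for per-protocol exclusions. Only the section 9 text is available here, so a further display defined elsewhere cannot be ruled out.

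**Conclusion.** The point holds for the planned laboratory analyses, not for laboratory safety reporting as a whole. As written in 9.2, they pool marginal with critical values, hide worsening within an out-of-range category, and average away a few large changes. The ANOVA does use the numeric change of subjects who start out of range, but only as part of the mean.

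In the illustrations, power on the mean is about 12% to 19% for 4 to 6 affected subjects in 200. These figures rest on the assumed SD of 2.5 and loss of 10 mmol/L. The structural point about the shift table needs no numerical assumption, except that ordinary reference ranges are narrower than the entry limits for some analytes.

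No primary conclusion changes. The plan should be amended because this is a declared safety endpoint and, according to section 4.1, critical alert levels already exist. The benefit is chiefly descriptive; the added display should not be presented as a powerful test.

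**What to change.** Keep the ANOVA and the existing shift table. In 9.2, add for the key electrolytes and renal measures:

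1. A shift from Visit 1 to the worst post-dose value at Visits 2 and 3, by arm, with the laboratory manual's critical alert levels as extra categories beyond low and high. Show the low and high directions separately where both matter.
2. The number and percent of subjects per arm with a new post-dose critical value, with the difference and its 95% CI. Fisher's exact test may be given as a descriptive aid.
3. The distribution, by arm, of each subject's largest adverse change from screening, shown separately for subjects out of range at Visit 1. This makes low-to-lower and high-to-higher changes visible, including an eGFR fall that crosses no category boundary.

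Where the manual gives no critical level for an analyte, the 3.5.2 limits may be shown, but labelled as outside entry limits and not as critical. Confirm which analytes the manual covers before fixing the table shells.

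The cost is a few more tables and more unadjusted safety comparisons, which should be labelled as such. No new samples, staff or clinical rules are needed.
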